### **2.3.2 Study periods**

This study will include 5 periods, a Screening Period (2 to 5 weeks), a double-blind Treatment Period (48 weeks; final dose at Week 44), an optional open-label extension (OLE) Period (96 weeks, final dose at Week 136 for subjects receiving bimekizumab 320mg Q8W and at Week 140 for subjects receiving bimekizumab 320mg Q4W, followed by a safety follow-up (SFU) Period (20 weeks after the final dose of IMP). Eligible subjects from US and Canada sites who have completed the OLE Period (at Week 144), including subjects in the SFU period and subjects who have completed the SFU Period will have the option to enroll in the 48-week Open-Label Extension 2 (OLE2) Period followed by a SFU Period (SFU2, 20 weeks after the final dose of IMP administered in the OLE2).

The double-blind treatment Period will be separated into an Initial Treatment Period (16 weeks) and a Maintenance Treatment Period (32 weeks). The end of the study is defined as the date of the last visit of the last subject in the study.

Subjects withdrawing early from the study will undergo the premature end of treatment (PEOT) Visit assessments and will enter the SFU Period. Following completion or early withdrawal from the OLE2 Period, subjects will undergo the SFU of the OLE2 Period (SFU2) and will return for the SFU2 Visit 20 weeks after the last dose of IMP administration in the OLE2 treatment period.

The following study periods are defined for the classification by study period:

- Screening Period: Prior to the date of first dose of study drug
- Initial Treatment Period is defined as the time from the first study drug administration up to the start of the Maintenance Treatment Period
- Maintenance Treatment Period starts with the first study drug administration at or after the Week 16 visit
- Open-Label Extension Period starts with the first study drug administration at or after the Week 48 visit
- SFU Period is 20 weeks after the final dose of IMP in the double-blind Treatment Period or Open-Label Extension Period
- Open-Label Extension 2 Period starts with the first study drug administration at or after the Week 144/OLE2 Baseline visit
- SFU2 Period is 20 weeks after the final dose of IMP in the OLE2.

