**Table 7-2: Dosing scheme, OLE Period**

Week	48 (1st OLE dose)	Year 2											Year 3													
		52	56	60	64 ab	68	72 ab	76	80	84 ac	88	92	96 ab	100	104	108 ac	112	116	120 ab	124	128	132 ac	136	140		
Bimekizumab 320mg Q4W	●●	●●	●●	●●	●●	●●	●●	●●	●●	●●	●●	●●	●●	●●	●●	●●	●●	●●	●●	●●	●●	●●	●●	●●	●●	●●
Bimekizumab 320mg Q8W	●●		●●		●●		●●		●●		●●		●●		●●		●●		●●		●●		●●		●●	

OLE=Open-Label Extension; Q4W=every 4 weeks; Q8W=every 8 weeks

Notes: A bimekizumab 160mg injection is depicted by a black circle (●).

a The subject's dosing interval will change from Q4W to Q8W at Week 64 or at the next scheduled clinic visit after implementation of Protocol Amendment 5.0 if the subject has already completed the Week 64 visit.

b Subjects whose dosing interval is changed to Q8W should be dosed at this visit and will receive kits for home administration 8 weeks later.

c Subjects whose dosing interval is changed to Q8W should NOT be dosed at this visit and will receive kits for home administration 4 weeks later.

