### 10.1.3.2 For subjects who switch from BKZ 320mg Q4W to Q8W at Week 16:

Study medication duration (days)

- Initial Treatment Period (attributed to BKZ 320mg Q4W)
  - Date of last dose in the Initial Treatment Period – date of first dose + 28 days

Note: If date of last dose in the Initial Treatment Period + 28 days extends to a date beyond the first dose in the Maintenance Treatment Period, then this calculation reverts to:

  - Date of first dose in the Maintenance Treatment Period – date of first dose + 1.
- Maintenance Treatment Period (attributed to BKZ 320mg Q8W)
  - Use the study medication duration algorithm specified for the Maintenance Treatment Period in Section 10.1.2
- Initial and Maintenance Treatment Period (attributed to Total BKZ)
  - Study medication duration in Initial Treatment Period + Study medication duration in Maintenance Treatment Period.

Time at risk (days)

- Initial Treatment Period (attributed to BKZ 320mg Q4W)
  - Date of first dose in the Maintenance Treatment Period - date of first dose + 1 day.
- Maintenance Treatment Period (attributed to BKZ 320mg Q8W)
  - Use the time at risk algorithm specified for the Maintenance Treatment Period in Section 10.1.2
- Initial and Maintenance Treatment Period (attributed to Total BKZ)
  - Use the time at risk algorithm specified for subjects who do not switch study treatments in Section 10.1.3.1

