#### 10.1.4.2 For subjects who switch from BKZ 320mg Q4W to Q8W during Open-Label Extension Period

Following Protocol Amendment 5.0, subjects receiving Q4W should switch to Q8W during the Open-Label extension period. (see Section 2.3.2.4 for further details).

Study medication duration (days)

- Attributed to BKZ 320mg Q4W:
  - Date of last BKZ 320mg Q4W dose in the OLE Period – date of first BKZ 320mg Q4W dose in the OLE Period + 28 days

Note: If date of last BKZ 320mg Q4W dose in the OLE Period + 28 days extends to a date beyond the date of first BKZ 320mg Q8W dose in the OLE Period, then this calculation reverts to:

- Date of first BKZ 320mg Q8W dose in the OLE Period – date of first BKZ 320mg Q4W dose in the OLE Period + 1.
- Attributed to BKZ 320mg Q8W use the minimum of:
  - Date of last BKZ 320mg Q8W dose in the OLE Period – date of first BKZ 320mg Q8W dose in the OLE Period + 56 days.
  - First dose date in Open-Label Extension Period 2 – date of first BKZ 320mg Q8W dose in the Open-Label Extension Period + 1.

Note: If date of last bimekizumab dose in the Open-Label Extension Period + 56 days extends to a date beyond the final visit date (including PEOT, but not including SFU), then this calculation reverts to:

- Final visit date (including PEOT, but not including SFU) – date of first BKZ 320mg Q8W dose in the OLE Period + 1.

Note: For subjects who die, if date of last bimekizumab dose in the Open-Label Extension Period + 56 days extends to a date beyond the date of death, then this calculation reverts to:

- Date of death – date of first BKZ 320mg Q8W dose in the OLE Period + 1.
- Attributed to Total BKZ
  - Sum of study medication duration in OLE period attributed to BKZ 320mg Q4W and study medication duration in OLE period attributed to BKZ 320mg Q8W-1.

Time at risk (days)

- Attributed to BKZ 320mg Q4W:
  - Date of first BKZ 320mg Q8W dose in the OLE Period – date of last BKZ 320mg Q4W dose in the OLE Period + 1 day
- Attributed to BKZ 320mg Q8W:
  - For all subjects, use the minimum of the following:
    - Date of last BKZ 320mg Q8W dose in the OLE Period – date of first BKZ 320mg Q8W dose in the OLE Period + 140 days.
    - Date of first BKZ 320mg Q8W dose in OLE2 - date of first BKZ 320mg Q8W dose in the Open-Label Extension Period + 1 day
    - Date of last clinical contact – date of first BKZ 320mg Q8W dose in the OLE Period + 1.
    - Date of death – date of first BKZ 320mg Q8W dose in the OLE Period + 1.

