##### Study medication duration (days)

Total study medication duration attributed to each dose will be obtained by summing the study medication duration(s) at each specific dose in each individual study period. Total study medication duration attributed to BKZ Total will be obtained by summing the study medication durations in each individual study period and deducting n-1, where n is the number of periods covered that are being summed.

Study medication duration at each specific dose in each individual study period is calculated separately as follows:

- Attributed to BKZ 320mg Q4W:

- Date of last consecutive BKZ 320mg Q4W dose in current study period – date of first consecutive BKZ 320mg Q4W dose in current study period + 28 days

Note: If date of last consecutive BKZ 320mg Q4W dose in current study period + 28 days extends to a date beyond the date of first BKZ 320mg Q8W dose in the next study period, then this calculation reverts to:

- Date of first BKZ 320mg Q8W dose in the next study period – date of first BKZ 320mg Q4W dose in the current study period.

Note: If BKZ 320mg Q4W is the last dosing schedule received in the last study period the subject receives bimekizumab in and date of last consecutive BKZ 320mg Q4W dose in current study period + 28 days extends to a date beyond the final visit date (including PEOT, but not including SFU), then this calculation reverts to:

- Final visit date (including PEOT, but not including SFU) – date of first BKZ 320mg Q4W dose in the current study period + 1.

Note: For subjects who die, where BKZ 320mg Q4W is the last dosing schedule received in the last study period the subject receives bimekizumab in and date of last consecutive BKZ 320mg Q4W dose in current study period + 28 days extends to a date beyond the date of death, then this calculation reverts to:

- Date of death – date of first BKZ 320mg Q4W dose in the current study period + 1.

- Attributed to BKZ 320mg Q8W

- Date of last consecutive BKZ 320mg Q8W dose in current study period – date of first consecutive BKZ 320mg Q8W dose in current study period + 56 days

Note: If date of last consecutive BKZ 320mg Q8W dose in current study period + 56 days extends to a date beyond the date of first BKZ 320mg Q4W dose in the next study period, then this calculation reverts to:

- Date of first BKZ 320mg Q4W dose in the next study period – date of first BKZ 320mg Q4W dose in the current study period.

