#### Time at risk (days)

Total time at risk attributed to each dose will be obtained by summing the time(s) at risk at each specific dose in each individual study period and deducting n-1, where n is the number of non-consecutive periods covered that are being summed. Total time at risk attributed to BKZ Total will be obtained by using the time at risk algorithms specified for subjects who do not switch study treatments in Section 10.1.5.1.

- Time at risk at each specific dose in each individual study period is calculated separately as follows:

- Attributed to BKZ 320mg Q4W:

- Date of first BKZ 320mg Q8W dose in the next study period – date of first BKZ 320mg Q4W dose in the current study period.

Note: If BKZ 320mg Q4W is the last dosing schedule received in the last study period, then this calculation reverts to:

- For all subjects, use the minimum of the following:
- Date of last BKZ 320mg Q4W dose in the current study period – date of first BKZ 320mg Q4W dose in the current study period + 140 days.
- Date of first BKZ 320mg Q8W dose in OLE2 - date of first BKZ 320mg Q4W dose in the Open-Label Extension Period + 1 day. The OLE and The OLE2 treatment periods should not overlap by more than 1 day
- Date of last clinical contact – date of first BKZ 320mg Q4W dose in the OLE Period + 1.
- Date of death – date of first BKZ 320mg Q4W dose in the current study period + 1

- Attributed to BKZ 320mg Q8W:

- Date of first BKZ 320mg Q4W dose in the next study period – date of first BKZ 320mg Q8W dose in the current study period.

Note: If BKZ 320mg Q8W is the last dosing schedule received in the last study period, then this calculation reverts to:

- For subjects who die

Date of death – date of first BKZ 320mg Q8W dose in the current study period + 1.

For all other subjects, use the minimum of the following:

- Date of last BKZ 320mg Q8W dose in the current study period – date of first BKZ 320mg Q8W dose in the current study period + 140 days.
- Date of first dose in OLE2 - date of first BKZ 320mg Q8W dose in the Open-Label Extension Period + 1 day.
- Date of last clinical contact – date of first BKZ 320mg Q8W dose in the OLE Period + 1.

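### SAP 10.1.4.2 counts Q4W time at risk for OLE switchers from the last Q4W dose, so it covers one dosing gap instead of the Q4W phase and inflates the Q4W exposure-adjusted rates in the OLS tables

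*SAP*

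**What the plan says.** Section 10.1.4.2 gives Q4W time at risk for OLE switchers as the first Q8W dose date – "date of last BKZ 320mg Q4W dose in the OLE Period + 1 day". The Amendment 4 entry for this section carries the same wording.

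The parallel rules start at a first dose:

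- Q4W study medication duration in 10.1.4.2 itself: when its cap applies, it ends in "date of first BKZ 320mg Q4W dose in the OLE Period + 1".
- Q4W time at risk for the Week 16 switch (10.1.3.2): "Date of first dose in the Maintenance Treatment Period - date of first dose + 1 day".
- Time at risk for OLE subjects who do not switch (10.1.4.1): every term is measured from the first OLE dose.
- Q4W time at risk in the BKZ Set (10.1.5.2): the date subtracted is the "date of first BKZ 320mg Q4W dose in the current study period".

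Section 10.2.1 makes these definitions the basis of the exposure-adjusted AE summaries. Sections 3.6 and 10.2 group OLE events by the dose most recently received, so events before the switch belong to Q4W.

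A second, smaller slip is in 10.1.5.2. When the Q8W study medication duration would run past the first Q4W dose of the next period, the fallback is the first "Q4W dose in the next study period – date of first BKZ 320mg Q4W dose in the current study period". The Q8W time-at-risk rule in the same section subtracts the first Q8W dose of the current period.

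**The concern.** Numerator and denominator cover different periods. Q4W events are collected from Week 48 to the switch, while Q4W person-time covers only the gap between the last Q4W dose and the first Q8W dose. Q8W time at risk in the same section starts at the first Q8W dose, so the bias falls on one column only and Q4W looks less safe relative to Q8W.

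The tables at stake are the OLS summaries per 100 subject-years in 10.2.2 (TEAEs, serious TEAEs, TEAEs leading to discontinuation) and the OLE safety topics of interest in 10.2.3. Exposure-adjusted TEAEs, SAEs and TEAEs leading to withdrawal are the secondary safety variables in 2.2.3.1. After Protocol Amendment 5.0, Q4W subjects in the OLE are expected to switch, so this rule covers the ordinary case.

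**Working it through.** The SAP states no OLE person-time or rate, so there is no figure of its own to reproduce. The check is date arithmetic on the schedule.

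**Inputs**

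- OLE start, Week 48 (2.3.2): "Open-Label Extension Period starts with the first study drug administration at or after the Week 48 visit".
- Switch visits (Table 7-2, footnote a): the "dosing interval will change from Q4W to Q8W at Week 64 or at the next scheduled clinic visit" after Amendment 5.0.
- Weeks 64, 72, 96 and 120 (footnote b): "Subjects whose dosing interval is changed to Q8W should be dosed at this visit". The gap from the last Q4W dose is 4 weeks if the visit dose is the first Q8W dose.
- Weeks 84, 108 and 132 (footnote c): no dose at the visit, next dose 4 weeks later, so the gap is 8 weeks.
- Assumption: dosing is on schedule.

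**Formulas** (F = week of first Q8W dose, L = week of last Q4W dose)

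- As written: (F – L) × 7 + 1
- From first Q4W dose: (F – 48) × 7 + 1

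| Switch visit | L | F | As written (days) | From first dose (days) | Ratio |
|---|---|---|---|---|---|
| 64 | 60 | 64 | 29 | 113 | 3.9 |
| 72 | 68 | 72 | 29 | 169 | 5.8 |
| 84 | 80 | 88 | 57 | 281 | 4.9 |
| 96 | 92 | 96 | 29 | 337 | 11.6 |
| 108 | 104 | 112 | 57 | 449 | 7.9 |
| 120 | 116 | 120 | 29 | 505 | 17.4 |
| 132 | 128 | 136 | 57 | 617 | 10.8 |

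**Other reading of a dosed switch visit.** If the dose at a footnote-b visit counts as the last Q4W dose, the first Q8W dose comes 8 weeks later:

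- Week 64: (72 – 64) × 7 + 1 = 57 against (72 – 48) × 7 + 1 = 169, ratio 3.0.
- Week 96: (104 – 96) × 7 + 1 = 57 against (104 – 48) × 7 + 1 = 393, ratio 6.9.

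**Do the parts add up?** Take a Week 96 switch, last dose at Week 136, full 140-day follow-up and no OLE2:

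- Total BKZ (10.1.4.1 rule): (136 – 48) × 7 + 140 = 756 days.
- Q8W: (136 – 96) × 7 + 140 = 420 days.
- Q4W as written: 29 + 420 – 1 = 448, so 756 – 448 = 308 days belong to neither dose.
- Q4W from first dose: 337 + 420 – 1 = 756, exact.
- Q4W study medication duration for this subject is (92 – 48) × 7 + 28 = 336 days, against a time at risk of 29.

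**From subject to table.** The Q4W column also holds subjects who stop before switching, counted from the first OLE dose. Their share is not given. Assume that they stop midway through the Q4W phase with 140 days of follow-up. For a Week 64 switch with 10% non-switchers, each of these contributes 16 × 7 / 2 + 140 = 196 days. The EAER factor is (0.9 × 113 + 0.1 × 196) / (0.9 × 29 + 0.1 × 196) = 121.3 / 45.7 = 2.7. With 5% to 20% non-switchers and switches at Weeks 64 to 96, the factor runs from 2.1 to 7.8.

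EAIR stops exposure at the first event (10.2.1). Take a constant hazard, switchers only, and subjects with an event contributing their time from the first Q4W dose. The EAIR factor is then 3.9 (Week 64) and 11.1 (Week 96) at 1 per 100 patient-years. At 200 per 100 patient-years it is 2.2 and 1.5.

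**The 10.1.5.2 slip.** The last active maintenance Q8W dose is at Week 40 (Table 7-1). Week 40 plus 56 days is Week 48, which is not beyond the first OLE dose, so on schedule the fallback is not triggered.

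**The case against.** The best defence is that this is a slip of one word. Four parallel rules show what was meant, and a careful programmer would notice. The intent is indeed clear. The SAP is nevertheless what the derivation is built from, and the Amendment 4 entry kept the wording.

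Several stronger readings are tempting, and the SAP does not support them:

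- *All OLE Q4W rates are 4 to 12 times too high.* That range is the ratio of time at risk for one subject who switches on schedule at Weeks 64 to 96, and it carries over only to the EAER of such switchers. Non-switchers dilute the column, and EAIR of common events moves much less. Later switches exceed 12, so that figure is not a ceiling either.
- *The rule governs nearly the whole Q4W denominator.* Switching is the expected course, but the SAP gives neither the mix of switch visits nor the share who stop first.
- *All bimekizumab safety rates are affected.* OLE Total BKZ uses 10.1.4.1, BKZ Set time at risk uses 10.1.5.2, and the comparisons with secukinumab use 10.1.1 to 10.1.3. None of these has the wrong start date.
- *The 10.1.5.2 slip is of equal weight.* It changes study medication duration only, which does not enter EAER or EAIR, and it matters only off schedule. It then calls for a Q4W dose date that a subject on Q8W throughout that period does not have.

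**Conclusion.** The Q4W time-at-risk rule in 10.1.4.2 is wrong as written and contradicts its own section and three others. It should be corrected before the OLE outputs are run.

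Per switcher, with on-schedule dosing and the first dose at or after the switch visit taken as the first Q8W dose, Q4W time at risk is understated about 4- to 12-fold for switches at Weeks 64 to 96 and about 17-fold at Week 120. Taking the dose at a dosed visit as the last Q4W dose lowers this to about 3.0 at Week 64 and 6.9 at Week 96.

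For the Q4W column of the OLS exposure-adjusted AE tables, the direction is certain (upward) but no single factor can be derived. The size depends on switch timing, the share of subjects who stop before switching, and how frequent the event is. The 10.1.5.2 slip is minor.

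**What to change.** - In 10.1.4.2, define Q4W time at risk for switchers as date of first Q8W dose in the OLE – date of first Q4W dose in the OLE + 1. On schedule this equals (week of first Q8W dose – 48) × 7 + 1. The week to use is that of the first Q8W dose, not of the switch visit.
- State whether the dose given at a dosed switch visit counts as Q4W or Q8W for this derivation.
- Add a programmed check that Q4W + Q8W – 1 equals Total BKZ for each switcher. For this to hold for deaths, add the missing + 1 to the death term in the 10.1.4.1 time-at-risk rule, which 10.1.4.2 already has.
- Minor: in the 10.1.5.2 Q8W duration fallback, subtract the first Q8W dose of the current study period instead of the first Q4W dose.

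The cost is SAP wording and a change to the derivations. No new data are needed and no dosing rule is touched. Any OLE output already run with the written rule needs its Q4W exposure-adjusted rates rerun.

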### **10.1.5 Exposure during the Double-blind and Open-Label Extension Period based on BKZ set**

Definitions for study medication duration (days) and time at risk (days) during the double-blind and Open-Label Extension Period are provided as follows:

#### **10.1.5.1 For subjects who do not switch dose**

For subjects randomized to bimekizumab 320mg Q4W at Baseline who continue on the Q4W dose schedule without switching:

##### Study medication duration (days)

- Date of last bimekizumab dose – date of first bimekizumab dose + 28 days
- Note: If date of last bimekizumab dose + 28 days extends to a date beyond the final visit date (including PEOT, but not including SFU), then this calculation reverts to:
  - Final visit date (including PEOT, but not including SFU) – date of first dose + 1.

Note: For subjects who die, if date of last bimekizumab dose + 28 days extends to a date beyond the date of death, then this calculation reverts to:

- Date of death – date of first dose + 1.

##### Time at risk (days)

- For all subjects, use the minimum of the following:
  - Date of last dose – date of first + 140 days.
  - Date of last clinical contact – date of first dose + 1.
  - Date of death – date of first dose + 1.

For subjects randomized to secukinumab at Baseline who initiate bimekizumab at Week 48 and continue on the same dose schedule in the OLE without switching, use the study medication duration and time at risk algorithms specified for subjects who do not switch study treatments in Section [10.1.4.1](#)

#### **10.1.5.2 For subjects who switch dose**

Subjects can switch bimekizumab 320mg dose schedule up to three times during the Double-blind and Open-Label Extension Period. Switches can occur at Week 16, Week 48, and Week 96 or at specific visits during the OLE following amendment 5.0. See Section [2.3.2](#) for further details regarding switching.

##### Study medication duration (days)

Total study medication duration attributed to each dose will be obtained by summing the study medication duration(s) at each specific dose in each individual study period. Total study medication duration attributed to BKZ Total will be obtained by summing the study medication durations in each individual study period and deducting n-1, where n is the number of periods covered that are being summed.

Study medication duration at each specific dose in each individual study period is calculated separately as follows:

- Attributed to BKZ 320mg Q4W:

- Date of last consecutive BKZ 320mg Q4W dose in current study period – date of first consecutive BKZ 320mg Q4W dose in current study period + 28 days

Note: If date of last consecutive BKZ 320mg Q4W dose in current study period + 28 days extends to a date beyond the date of first BKZ 320mg Q8W dose in the next study period, then this calculation reverts to:

- Date of first BKZ 320mg Q8W dose in the next study period – date of first BKZ 320mg Q4W dose in the current study period.

Note: If BKZ 320mg Q4W is the last dosing schedule received in the last study period the subject receives bimekizumab in and date of last consecutive BKZ 320mg Q4W dose in current study period + 28 days extends to a date beyond the final visit date (including PEOT, but not including SFU), then this calculation reverts to:

- Final visit date (including PEOT, but not including SFU) – date of first BKZ 320mg Q4W dose in the current study period + 1.

Note: For subjects who die, where BKZ 320mg Q4W is the last dosing schedule received in the last study period the subject receives bimekizumab in and date of last consecutive BKZ 320mg Q4W dose in current study period + 28 days extends to a date beyond the date of death, then this calculation reverts to:

- Date of death – date of first BKZ 320mg Q4W dose in the current study period + 1.

- Attributed to BKZ 320mg Q8W

- Date of last consecutive BKZ 320mg Q8W dose in current study period – date of first consecutive BKZ 320mg Q8W dose in current study period + 56 days

Note: If date of last consecutive BKZ 320mg Q8W dose in current study period + 56 days extends to a date beyond the date of first BKZ 320mg Q4W dose in the next study period, then this calculation reverts to:

- Date of first BKZ 320mg Q4W dose in the next study period – date of first BKZ 320mg Q4W dose in the current study period.

Note: If BKZ 320mg Q8W is the last dosing schedule received in the last study period the subject receives bimekizumab in and date of last consecutive BKZ 320mg Q8W dose in current study period + 56 days extends to a date beyond the final visit date (including PEOT, but not including SFU), then this calculation reverts to:

- Final visit date (including PEOT, but not including SFU) – date of first BKZ 320mg Q8W dose in the current study period + 1.

Note: For subjects who progress into the OLE2, if date of last bimekizumab dose in the Open-Label Extension Period + 56 days extends to a date beyond the date of first dose in the Open-Label Extension 2 Period then this calculation reverts to:

- First dose date in Open-Label Extension 2 Period – date of first BKZ 320mg Q8W dose in the current study period + 1.

Note: For subjects who die, where BKZ 320mg Q8W is the last dosing schedule received in the last study period the subject receives bimekizumab in and date of last consecutive BKZ 320mg Q8W dose in current study period + 56 days extends to a date beyond the date of death, then this calculation reverts to:

- Date of death – date of first BKZ 320mg Q8W dose in the current study period + 1.

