### 10.1 Extent of exposure

Summaries for exposure will be provided for the SS, MS, OLS, OLS2, and BKZ set. These consist of a descriptive summary of study medication duration in days. In addition, total study medication duration and time at risk will be summarized in years by treatment group

The cumulative study medication duration will be summarized for the SS for subjects exposed for given durations of time, the following categories for duration will be used:

- >0 weeks
- >=16 weeks

- $\geq 24$  weeks
- $\geq 48$  weeks

For the Week 144 analysis and for the final analysis, the table will also be created for the BKZ set and will include the above categories plus the below categories. A bimekizumab total column will also be displayed.

- $\geq 72$  weeks
- $\geq 96$  weeks
- $\geq 120$  weeks
- $\geq 144$  weeks

In addition, the OLE2 exposure will be displayed separately as follow:

- $> 0$  weeks
- $\geq 16$  weeks
- $\geq 24$  weeks
- $\geq 48$  weeks.

Definitions for study medication duration and time at risk in days are provided below. Time at risk will be summarized in years. Time at risk in years is calculated by dividing the time at risk in days by 365.25.

Throughout this section, date of last clinical contact for each subject is defined as the maximum of (last visit date including SFU or SFU2 visit, last imputed AE start date, date of study termination or completion, last date of study drug administration).

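### SAP 10.1.5.2 deducts n-1 days from period durations that share no day on schedule, so a standard on-schedule dose switcher is reported at 1006 days and misses the ≥144 weeks row

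*SAP*

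**What the plan says.** SAP 10.1.5.2 covers subjects who change bimekizumab dosing interval. It computes a duration for each dose in each study period and forms BKZ Total by "summing the study medication durations in each individual study period and deducting n-1". The only description of n is that it counts the periods entering the sum.

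The components are:
- Q4W segment: last dose minus first dose, plus 28 days.
- Q8W segment: last dose minus first dose, plus 56 days.
- Q4W segment that would run past a Q8W start in the next period: "Date of first BKZ 320mg Q8W dose in the next study period – date of first BKZ 320mg Q4W dose in the current study period", with no +1.

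Other sections treat the same join differently:
- 10.1.5.1 (no switch): one span, last dose minus first dose plus 28, no deduction.
- 10.1.3.2 (Initial plus Maintenance, Total BKZ): a plain sum with no deduction, although its reversion formula does carry a +1.
- 10.1.4.2 (switch within the OLE): the reversion formula carries a +1, and the total is the Q4W duration plus the "study medication duration in OLE period attributed to BKZ 320mg Q8W-1".

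On reporting, 10.1 states: "For the Week 144 analysis and for the final analysis, the table will also be created for the BKZ set". That table adds rows up to ≥144 weeks and has a bimekizumab total column.

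**The concern.** Subtracting one day per join corrects a double count. If no day is counted twice, it removes real exposure. The loss is only a day or two, but the row limits at 48, 96 and 144 weeks coincide with planned period ends, so a day or two decides which row a subject falls in.

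Only subjects randomized to bimekizumab can reach 144 weeks. Protocol Amendment 5.0 moves the remaining Q4W subjects to Q8W, so 10.1.5.2 governs nearly all of those who could be in the top row. At stake is the reported number of subjects with full-length bimekizumab exposure.

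**Working it through.** **Inputs**, with first dose = day 0 and 7 days per week:
- Last Initial dose Week 12 (day 84); first Maintenance dose Week 16 (day 112), from Table 7-1.
- Last active Maintenance dose: Week 40 on Q8W (day 280), because Week 44 is placebo (2.3.2.3); Week 44 on Q4W (day 308).
- First OLE dose Week 48 (day 336). Last OLE dose Week 136 on Q8W (day 952) or Week 140 on Q4W (day 980), from 2.3.2.
- Row limit: 144 × 7 = 1008 days.

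**Reproducing the plan's own figures.** Initial period: 84 − 0 + 28 = 112 days, as stated in 10.1.1. Week 48 = 48 × 7 = 336 days, as in 4.2.1.7.2.

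**Switch between periods, on schedule.**
- Initial: 84 − 0 + 28 = 112 (days 0 to 111).
- Maintenance on Q8W: 280 − 112 + 56 = 224. On Q4W: 308 − 112 + 28 = 224 (days 112 to 335).
- OLE on Q8W: 952 − 336 + 56 = 672 (days 336 to 1007).
- Sum: 112 + 224 + 672 = 1008, with no day in two periods.
- Reported: 1008 − (3 − 1) = 1006, or 143.7 weeks.

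**Non-switcher, same span (10.1.5.1).** 980 − 0 + 28 = 1008, inside the row.

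**Switch inside the OLE.**
- At Week 72: Q4W 476 − 336 + 28 = 168; Q8W 952 − 504 + 56 = 504; OLE total 672; sum 1008. Switches at Weeks 64, 96 and 120 also sum to 1008.
- Reported: 1006 if n counts the three study periods, 1005 if n counts the four dose-by-period segments.
- At Week 84: no dose at that visit (Table 7-2, footnote c), so the last Q4W dose is Week 80 and the first Q8W dose Week 88. Q4W 560 − 336 + 28 = 252; Q8W 952 − 616 + 56 = 392; sum 112 + 224 + 252 + 392 = 980. Weeks 108 and 132 also give 980. Reported: 978 or 977. These subjects miss the row with or without the deduction.

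**Conflict at 48 weeks.** An on-schedule Q4W/Q8W subject who stops at Week 48 has 112 + 224 = 336 days (48 weeks) under 10.1.3.2 but 336 − 1 = 335 under 10.1.5.2. The ≥48 weeks row appears in both the SS and the BKZ set tables.

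**Off-schedule visits.**
- Last OLE dose 2 days late and final visit 1 day late (Q4W/Q8W/Q8W): the final-visit cap applies, so OLE = 1009 − 336 + 1 = 674, and the total is 112 + 224 + 674 − 2 = 1008. In the row.
- Both 14 days late: 112 + 224 + 686 − 2 = 1020. In the row.
- Week 48 visit 7 days early, Q8W continuing: Maintenance stays at 224 because no truncation is written for an unchanged regimen, and OLE = 952 − 329 + 56 = 679. The sum is 1015 for a 1008-day span. Seven days are counted twice and two are removed, so 1013 is reported.

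**Share of Q4W/Q8W/Q8W completers at ≥1008 days**, from simulation with the 3.1 windows (±3, ±7, ±14 days) and the 10.1.5.2 caps, as written versus with only the deduction removed:
- every visit on the planned day: 0% versus 100%;
- 90% chance per visit of being on the day: 7–8% versus 75–77%;
- 70% chance: 17% versus 48–50%;
- uniform over the windows: 22–23% versus 29%.

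The ranges come from two independent runs.

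**The case against.** The strongest reply is that this is 2 days in 1008 (0.2%), in one descriptive row, at a limit set exactly at the nominal treatment length. With visits uniform over the windows, about 71% of these completers miss the row even without the deduction, because of the limit itself and the final-visit cap. The 0% versus 100% case is a knife edge, and the adherence levels are invented. Week 136 is not a scheduled clinic visit, so applying visit windows to that dose is a further assumption. All of this stands and limits the size of the point. It does not make the deduction consistent with the formulas it is applied to.

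A reader might infer more than the SAP supports:
- *That every on-schedule switcher gets 1006 and the row is emptied.* Switchers at Weeks 84, 108 and 132 total 980 before any deduction. Slightly late, in-window visits and Q4W non-switchers do reach 1008, although under Protocol Amendment 5.0 few such non-switchers should complete.
- *That periods never overlap.* True on schedule and at the capped Q4W-to-Q8W join. Where the regimen is unchanged across periods, an early visit creates real overlap, which n-1 does not match either.
- *That long-term adverse event rates are distorted.* Those rates use time at risk (10.2.1), and 10.1.5.2 takes BKZ Total time at risk from 10.1.5.1 without this deduction.
- *That 10.1.4.2 pushes OLE switchers below a 96-week row.* An uncapped on-schedule switcher does get 672 − 1 = 671 days, but 10.1 specifies the ≥96 weeks row for the BKZ set, not the OLS.

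**Conclusion.** The point holds in limited form. The n-1 rule in 10.1.5.2 does not match that section's period formulas and disagrees with 10.1.5.1 and 10.1.3.2 for the same treatment span. It takes 2 days (or 3, depending on how n is read) from the standard on-schedule switcher and so leaves that subject out of the ≥144 weeks row.

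The deduction undercounts the row. The size depends on visit adherence, which the SAP does not give: about 6 to 7 percentage points with visits uniform over the windows, and more the closer conduct is to schedule. These shares isolate the deduction for one sequence and include no added truncation. They also assume that weeks are days divided by 7 without rounding, since the SAP gives no conversion for these categories. The consequence is confined to exposure reporting; it is worth correcting before the tables are run, but no efficacy result or BKZ Total event rate depends on it.

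**What to change.** In 10.1.5.2:
- Delete the n-1 deduction for BKZ Total study medication duration. This also removes the need to define n there.
- End every dose-by-period segment at the first dose of the next segment, without +1, including where the same regimen continues and where the switch falls inside the OLE.
- Keep the existing caps at final visit, first OLE2 dose and death.

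Both changes are needed. In the early Week 48 example, deleting the deduction alone would report 1015; with truncation, Maintenance is 329 − 112 = 217 and the total is 112 + 217 + 679 = 1008. Because truncation lowers some totals, the net change in the row count has to be read from the data.

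In 10.1.4.2, subtract 1 only when the capped +1 formula was used for the Q4W segment, or drop both the +1 and the −1.

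If a single first-to-last-dose span is preferred, the SAP should say that it also credits uncovered gap days: it would move the Week 84, 108 and 132 switchers from 980 to 1008. State the days-to-weeks conversion for the exposure rows as well.

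The cost is SAP wording and a small change to the exposure derivation, with no change to data collection.
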